4.3. Prior and Concomitant Medications

All medications taken from the time of informed consent to the final study visit, including medications that were started before the study and are ongoing during the study, will be reported in Concomitant Medications CRF.

All medications will be dictionary coded using the World Health Organization-Drug Dictionary (WHO-DD) to both an anatomic category and a therapeutic category, with the version in effect at the time of the first database lock. Drug names will be matched to respective Anatomical-Therapeutic-Chemical (ATC) classification, although a drug can be matched to more than one ATC classification (i.e. patients can be counted in several categories for the same medication). Prior medications, concomitant medications, and post-treatment medications are defined below and will be applied in the respective treatment periods (DBTP and SBTP).

- Prior medications are defined as medications for which the stop date is before the date of the first DBTP study treatment administration.
- Concomitant medications are defined as medications that are administered to the patients during the respective study treatment periods. Specifically:
 - Start date of the concomitant medication is on or after the first study treatment administration in respective study treatment periods (\geq DBTP Day 1 or \geq SBTP Week 12); **or**
 - Start date of the concomitant medication is before the first study treatment administration in respective study treatment periods and is “Ongoing” during the treatment emergent period; **or**
 - Start date of the concomitant medication is before the first study treatment administration in respective study treatment periods, and the end date is on or after the first study treatment administration in respective study treatment periods (\geq DBTP Day 1 or \geq SBTP Week 12).

The concomitant medication treatment emergent periods are defined as:

- For concomitant medications in the DBTP, the treatment emergent period is defined from the first day of double-blind study treatment administration to the last day of double-blind study treatment +168 days (for patients who do not continue into the SBTP) or to the day before the first single-blind study treatment administration (for patients who enter the SBTP).
- For concomitant medications in the SBTP, the treatment emergent period is defined from the first day of single-blind study treatment administration to the last day of single-blind study treatment +168 days.

Note: In the case the start date is before first DBTP study treatment administration and both ongoing status and stop date are missing, the medication will be assumed to be concomitant.

- Post-treatment medications are defined as medications for which the start date is after last date of study treatment administration +169 days (\geq last study treatment +169 days).

4.4. Prohibited Medications and Procedures During Study

The definitions of prohibited medications and procedures are described in the Section 7.8.1 of the protocol. They will be reviewed and identified by the study clinician and reported in protocol deviations.

4.5. Patient Disposition

Patient disposition will include the description of patient status at major milestone decisions in the study, as well as the patient analysis populations.

For patient study status, patient double-blind treatment period milestone categories are defined below. As applicable, percentages will be calculated using the number of randomized patients in the denominator, with two exceptions. Specifically, the two exceptions will be for the screened and non-randomized categories, which will not have associated percentages shown.

- The total number of screened patients, defined as originally having met the inclusion criteria and signed the ICF.
- The total number of randomized patients, defined as all screened patients with a double-blind treatment kit number allocated and recorded in the IVRS database, regardless of whether the treatment kit was used.
- The total number of patients randomized but not receiving study treatment.
- The total number of patients randomized and receiving study treatment.
- The total number of patients who completed the DBTP as collected on the End of Treatment e-CRF.
- The total number of patients who completed the DBTP, defined as at least 12 weeks of study treatment exposure and visit week 12 performed.

- The total number of patients who prematurely discontinued study treatment during the double-blind period, and the reasons for discontinuation collected on the End of Treatment e-CRF.
- The total number of patients who do not proceed into SBTP and complete the last study follow-up visit (i.e. End of Study/Visit 18).

Patient SBTP milestone categories are defined below. As applicable, percentages will be calculated using a denominator of the number of patients administer single-blind study treatment.

- The total number of patients receiving single-blind study treatment.
- The total number of patients ongoing in SBTP (applicable for the interim and first step analyses)
- The total number of patients who completed the SBTP as collected on the End of Treatment e-CRF.
- The total number of patients who completed the SBTP, defined as at least 24 weeks of study treatment exposure and week 24 visit performed.
- The total number of patients who prematurely discontinued study treatment during the SBTP, and the reasons for discontinuation collected on the End of Treatment e-CRF.
- The total number of patients from SBTP who complete the last study follow-up visit (i.e. End of Study/Visit 18).

The following patient populations for analyses are defined below:

- Randomized population
- Full analysis set population
- Double-blind safety analysis set
- Single-blind safety analysis set
- Anti-evinacumab antibody (ADA) analysis set
- Pharmacokinetic (PK) analysis set and total target analysis set
- PRO analysis set
- PET analysis set
- MRI analysis set

The following patient listings will provide the details from the patient disposition table.

- A listing of patients treated but not randomized, patients randomized but not treated, and patients randomized but not treated as randomized.
- A listing of patients prematurely discontinued from treatment, along with reasons for discontinuation.

4.6. Study Treatment Exposure and Compliance Variables

Study treatment exposure variables for infusions administered during the DBTP are listed below with associated definitions:

- Patient duration of double-blind study treatment exposure in weeks defined as: (last double-blind study treatment administration date +28 – first double-blind study treatment administration date)/7, regardless of unplanned intermittent discontinuations. Values will be rounded to one decimal place.
- The total number of double-blind study treatment infusions by patient.
- The following categories will be used for treatment exposure intervals: ≥ 1 day and <4 weeks, ≥ 4 weeks and <8 weeks, ≥ 8 weeks and <12 weeks, ≥ 12 weeks

Study treatment exposure variables for infusions administered during the SBTP are listed below with associated definitions:

- Patient duration of single-blind study treatment exposure in weeks defined as: (last single-blind evinacumab treatment administration date +28 – first single-blind evinacumab treatment administration date)/7, regardless of unplanned intermittent discontinuations. Values will be rounded to one decimal place.
- The total number of single-blind evinacumab treatment infusions by patient.
- The following categories will be used for treatment exposure intervals: ≥ 1 day and <4 weeks, ≥ 4 weeks and <8 weeks, ≥ 8 weeks and <12 weeks, ≥ 12 weeks

Study treatment exposure variables combining DBTP and SBTP are listed below for all patients who received evinacumab in the DBTP:

- Cumulative patient duration of evinacumab exposure in weeks defined as: double-blind treatment exposure plus single-blind treatment exposure, regardless of unplanned intermittent discontinuations.
- Cumulative total number of evinacumab treatment infusions by patient defined as: total number of double-blind infusions plus total number of single-blind infusions.
- The following categories will be used for cumulative patient treatment exposure intervals: ≥ 1 day and <4 weeks, ≥ 4 weeks and <8 weeks, ≥ 8 weeks and <12 weeks, ≥ 12 weeks and <16 weeks, ≥ 16 weeks and <20 weeks, ≥ 20 weeks and <24 weeks, ≥ 24 weeks

With respect to patient treatment administration compliance, the study treatment is administered during the investigative site visits and therefore study compliance will be assessed by infusion frequency for respective treatment periods, specifically:

- DBTP: for each patient as the average number of days between 2 infusions: (last double-blind dose date – first double-blind dose date) / (number of infusions in DBTP -1), for patients receiving at least 2 infusions.

- SBTP: for each patient as the average number of days between 2 infusions: (last single-blind dose date – first single-blind dose date) / (number of infusions in SBTP -1), for patients receiving at least 2 infusions.

All important and minor protocol deviations potentially impacting efficacy analyses, randomization and drug-dispensing irregularities, as well as other deviations, will be collected and reviewed on an ongoing basis throughout the study as described in the Protocol Deviation Plan (PDP). Both monitoring collected and programmatically derived deviations are listed and defined in the PDP.

4.7. Efficacy Variables

Efficacy will be assessed through the following measurements:

- **Lipids:** LDL-C (Ultracentrifugation), HDL-C, total-C, fasting TG, non-HDL-C (calculated by subtracting HDL-C from Total-C), Apo B, Apo A1, Apo CIII, Apo B/Apo A1 ratio, and Lp(a)
- **Other variables:** Hemoglobin A1c, hs-CRP, post heparin LPL activity, APOC2, APOA5, and metabolic parameters
- **Imaging:** F-FDG-PET, DW-MRI, and T2-MRI

The baseline value, unless noted otherwise, is defined as the last available measurement prior to the date of the first double-blind study treatment administration (applicable to measurement derivations during both DBTP and SBTP). For patients randomized and not treated, the baseline value is defined as the last available value prior to the date of randomization.

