4.2. Primary and Secondary Endpoints

4.2.1. Primary Endpoint

The primary endpoint is the percent lowering of TG levels from baseline following 12 weeks of repeated IV doses of evinacumab in the subset of patients with a documented history of sHTG (TG ≥ 1000 mg/dL [11.3 mmol/L]), a TG level of at least 500 mg/dL (5.6 mmol/L) at screening, a history of acute pancreatitis, and without LOF mutations in genes in the LPL pathway. (For patients randomized to evinacumab, baseline is defined as the period prior to the double-blind period; for patients randomized to placebo, baseline is defined as the period prior to the single-blind period.)

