10.4.3.2. Secondary and Exploratory Efficacy Analysis

Continuous secondary and exploratory endpoints will be analyzed similarly to the primary endpoint, except PP will not be computed. Binary endpoints will be summarized by counts and percents. Triglyceride mean percent change from baseline at each observation week will be summarized. Triglyceride mean percent change from baseline at each observation week will be analyzed and estimated for genetic mutations affecting LPL function (eg, homozygous LPL null [total LOF], heterozygous LPL null, with no LPL null gene mutations subgroups).

For the FDG-PET endpoint, comparisons will be within the evinacumab-treated patients in the double-blind period (week 12 vs week -2 for post/pre) and between the treatment groups in the double-blind period (week 12 vs week -2 for evinacumab in comparison to week 12 vs week -2 for placebo). In order to yield corresponding results, the MRI readout will be analyzed similarly as the FDG-PET endpoint. In addition, combining all evinacumab post/pre observations from the double-blind period (week 12 vs week -2) and the single-blind post/pre (week 24 vs week 12) for the patients who received placebo in the double-blind period, and post/pre (week 24 vs week -2 and week 24 vs week 12) for patients randomized to evinacumab during the double-blind period.

Summary statistics may be computed for time points beyond week 12 for the TG and continuous and exploratory endpoints in the patients randomized to evinacumab.

Summary statistics will be computed for the End of Day symptom diary and the symptom and dietary impact measure. These measures will also be psychometrically analyzed; this will be outlined in a separate psychometric analysis plan.

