4.7.2. Lipids Variables

Potential clinical benefits of study treatment will be explored through the following lipids parameters: LDL-C (Ultracentrifugation), HDL-C, total-C, fasting TG, non-HDL-C, Apo B, Apo A1, Apo CIII, Apo B/Apo A1 ratio, and Lp(a).

Baseline TG is defined as the mean of the last 2 measurements during the placebo run-in (day -28, day -14) and week 0.

Lipids parameters will be collected in a fasted state over the course of the study at time points listed in [Appendix 10.4](#), and sent to the central laboratory for evaluation, including scheduled and unscheduled blood draws. Both the absolute change from baseline and the percent change from baseline will be calculated for each lipids parameter, and derivations will be presented in

both international and conventional units. TG measurements with missing fasting status will be excluded from the summaries.

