5.7.1. Analysis of Primary Efficacy Variable

The primary efficacy analysis will assess within-patient percent change in TG over 12 weeks of evinacumab treatment (double-blind period for patients randomized to evinacumab and single-blind period for patients randomized to placebo).

The point estimates of TG percent changes between the placebo period and each observation week will be calculated using a Mixed-effect Model for Repeated Measures (MMRM) method in the FAS population. A natural log transformation will be applied to the TG levels prior to

analysis, aiming to provide a relatively normal data distribution (residuals will be examined for normality prior to proceeding with the analysis). The MMRM model will assess within-patient treatment comparisons (using an unstructured covariance matrix), while accounting for baseline TG, study visit, and baseline TG by study visit interaction. Note that study visits will be adjusted to start of evinacumab in order to pool data from both randomized groups of patients for this analysis. Since the comparison of study visits yields the within-patient comparisons of study treatments (ie, week 12 [after 12 weeks of treatment with evinacumab] compared to baseline at week 0 [after 4 weeks of treatment with placebo] for patients randomized to evinacumab and week 24 [after 12 weeks of treatment with evinacumab] compared to baseline at week 12 for those randomized to placebo), contrast and estimate statements will be used to assess treatment effects (least squares [LS] means with confidence intervals) and comparisons (LS mean ratio with CI). Within-patient comparisons will include all patients. In the event the MMRM model covariance matrix does not converge or normality is not achieved with the natural log transformation, then other transformations will be explored, including ranks.

To reduce variability of TG baseline measurements, baseline at week 0 for patients randomized to active treatment is the mean of the 3 log-transformed measurements at day -28, day -14, and week 0. Baseline at week 12 for patients switching from placebo to active is the mean of 3 log-transformed measurements at weeks 6, 8, and 12. Additional exploratory analyses may be carried out using the average of all available TG observations prior to first dose of active treatment, if no trend over time in those measurements is discernable.

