The estimate of the log TG mean ratio (week 12/baseline at week 0 for patients randomized to evinacumab and week 24/baseline at week 12 for those randomized to placebo) and the log of the standard deviation derived from the MMRM model (ie., LS mean ratio with CI) based on observed results from the patients without LOF mutations in genes in the LPL pathway will be reviewed for 40% reduction.

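### Outside the primary triglyceride model, the SAP measures single-blind change in placebo-first patients from the pre-double-blind baseline, so 12 weeks on placebo are mixed into it

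*SAP*

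**What the plan says.** **Protocol.** For the primary endpoint (4.2.1), "for patients randomized to placebo, baseline is defined as the period prior to the single-blind period". Section 3.2.1 says the same of TG in general: in patients given placebo in the double-blind period, the geometric mean of weeks 6, 8 and 12 is the baseline for the single-blind period. Section 10.4.3.2 states that "Continuous secondary and exploratory endpoints will be analyzed similarly to the primary endpoint, except PP will not be computed". For MRI it names the contrast: "the single-blind post/pre (week 24 vs week 12) for the patients who received placebo in the double-blind period". A common week-0 baseline appears in 10.4.3.1 only as a sensitivity analysis of TG.

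**SAP, primary TG model (5.7.1).** This follows the protocol. Visits are realigned to the start of evinacumab, the estimate uses "week 24/baseline at week 12 for those randomized to placebo", and "Baseline at week 12 for patients switching from placebo to active is the mean of 3 log-transformed measurements at weeks 6, 8, and 12".

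**SAP, everything else.** Section 4.7 says: "The baseline value, unless noted otherwise, is defined as the last available measurement prior to the date of the first double-blind study treatment administration", and adds that this is "applicable to measurement derivations during both DBTP and SBTP". Section 4.7.2 says: "Baseline TG is defined as the mean of the last 2 measurements during the placebo run-in (day -28, day -14) and week 0", with no week-12 alternative. Section 4.7.5 (mean of two pre-double-blind scans) and 4.11 (PRO) carry the same extension to both periods. Biomarkers (4.12, 5.12) have no baseline of their own and fall under the default in 6.1.

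**The concern.** Apart from the secondary TG and MRI endpoints, which protocol 4.2.2 defines by weeks of evinacumab treatment, the single-blind period has one stated purpose for the placebo arm: protocol 3.2.1 says it allows a treatment effect to be analysed in those patients. A change measured from before the double-blind period does not isolate that effect.

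Two consequences follow for the descriptive single-blind tables.

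- In placebo-first patients, change at weeks 16, 20 and 24 contains whatever happened between week 0 and week 12 on placebo. It can inflate the apparent effect or hide it.
- The all-patients column puts patients with 4, 8 and 12 weeks on drug beside patients with 16, 20 and 24 weeks on drug under the same visit label.

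For TG, the lipid tables and the primary model would report different week-24 changes for the same patients, with nothing in the SAP to explain why.

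**Working it through.** **1. Baseline for placebo-first patients in the single-blind period, by endpoint**

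| Endpoint | Protocol | SAP | Result |
|---|---|---|---|
| TG, MMRM and cohort extension | Weeks 6, 8, 12 (3.2.1, 10.4.3.1) | Weeks 6, 8, 12 (5.7.1, 5.7.1.1) | Agree |
| TG, descriptive | Weeks 6, 8, 12 (3.2.1) | Day -28, day -14, week 0 (4.7.2, 5.7.2) | Contradict |
| MRI | Week 24 vs week 12 (10.4.3.2) | Mean of two pre-double-blind scans (4.7.5, 5.7.5) | Contradict |
| Other lipids, other variables, PRO, biomarkers | As for the primary endpoint (10.4.3.2) | Last pre-double-blind value (4.7, 4.11, 6.1) | Conflict by inference |
| PET | Last scan at week 12 | Same | Not affected |
| Post-heparin LPL activity | Visits 2 and 13 only | Same | No week-12 value exists |

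**2. Disclosure.** SAP 1.2.4 item 4 covers arithmetic versus geometric averaging of the TG baseline. Item 5 deletes the sentence on analysing secondary endpoints like the primary, because the MMRM may not converge. Convergence is a reason to change the model, not the reference value. Neither item mentions a new baseline.

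**3. The plan's own figure.** Protocol 10.2 and SAP 2.2 give 80% power for within-patient MRI change with N=24, SD 5.96, true change 3.12 and one-sided alpha 0.05. For a paired t-test the noncentrality is (3.12/5.96) × √24 = 2.565 on 23 degrees of freedom, which gives 80.0%. The figure reproduces. The same paragraph has 16 evinacumab and 8 placebo patients, and 16 + 8 = 24, so the calculation counts the placebo-first patients' single-blind pre/post pairs. That fits the week 24 vs week 12 contrast. It contains no drift term.

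**4. Size.** Let e be the true reduction from the pre-evinacumab value and d the proportional change from week 0 to week 12 on placebo. The documents give no value for d, so ±20% is an assumption.

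- Placebo-first patients, week 24 vs week 0: apparent reduction = 1 − (1 + d)(1 − e)
- All patients at 2:1, geometric mean, same e in both sequences: apparent reduction = 1 − (1 − e)(1 + d)^(1/3)

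With e = 40%:

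| d | Placebo-first | All patients |
|---|---|---|
| −20% | 1 − 0.8 × 0.6 = 52% | 44.3% |
| −10% | 1 − 0.9 × 0.6 = 46% | 42.1% |
| 0 | 40% | 40.0% |
| +10% | 1 − 1.1 × 0.6 = 34% | 38.1% |
| +20% | 1 − 1.2 × 0.6 = 28% | 36.2% |

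Measured from week 12, every row returns 40%. The same expressions apply to any endpoint analysed as a ratio; TG is used because 40% is the plan's own target.

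**The case against.** A reader might infer that the SAP counts placebo drift as drug effect throughout, including in the main TG result. The documents do not support that. SAP 4.7 applies unless noted otherwise, and 5.7.1 notes otherwise. The realigned model estimates TG change at each observation week in the whole FAS, and 5.7.1.1 extends it to the cohorts. Placebo-first patients receive only 12 weeks of evinacumab, so the model covers all their time on drug. Model-based secondary TG results by week and cohort are therefore protected too.

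Other points on that side also carry weight.

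- The single-blind lipid, other-variable and PRO summaries are descriptive and also shown by double-blind arm, and week-12 change in the placebo arm is reported. The drift is visible at group level. It still cannot be taken out of the tables: arithmetic mean percent changes, medians and quartiles at weeks 12 and 24 do not subtract to give within-patient change from week 12.
- Protocol 4.2.2 labels the MRI baseline as the placebo run-in, which the SAP follows. But 10.4.3.2 is the analysis section and names week 24 vs week 12 for these patients, so the protocol itself needs both readings reconciled.
- Protocol 10.6 has a general rule of the latest valid pre-dose value without saying which dose, and for the questionnaires 10.4.3.2 plans summary statistics only. For endpoints other than TG and MRI, the conflict therefore rests on one general sentence in 10.4.3.2. This stands, and makes the case weaker there.
- SAP 1.2.4 item 5 does disclose that this sentence was dropped. Only the baseline consequence is missing.

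**Conclusion.** The point holds for the descriptive single-blind change-from-baseline results outside the primary TG model: lipids including TG, MRI, PRO, other variables and biomarkers. It is a direct contradiction of the protocol for descriptive TG and for MRI, and an inferred one elsewhere. At 2:1 allocation it touches about a third of patients, some 17 of 50.

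The primary TG estimate, the model-based TG results by week and cohort, PET and every sample-size figure are unchanged. Nor should the effect be read as a bias in favour of the drug: the direction depends on the sign of the drift, which the documents do not give. The range of 52% to 28% (about 44% to 36% for all patients) illustrates an assumed ±20% and is not a forecast. The all-patient figures also assume that 2:1 is retained at week 24 and that the true reduction is equal in the two sequences.

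**What to change.** In SAP 4.7, 4.7.2, 4.7.5, 4.11 and 6.1, state that for patients randomised to placebo the single-blind baseline is the last value before first evinacumab. For TG this is the mean of the log values at weeks 6, 8 and 12, as in 5.7.1; for MRI it is the week-12 scan. In addition:

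- keep change from the pre-double-blind baseline as a supportive display;
- present pooled single-blind results by weeks since first evinacumab;
- state that post-heparin LPL activity has no week-12 sample and so keeps its visit 2 baseline (the other lipase assays on the same two visits share this limit);
- list any departure that is intended in SAP 1.2.4, with its reason.

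No new data are needed. The week-12 lipid, MRI and PRO assessments are scheduled, and the schedule footnotes place assessments and imaging before that visit's infusion. The cost is extra derivations and tables, and a noisier MRI baseline in these patients. As a rough guide, if the 18% test/re-test variability in protocol 8.2.4.2 is read as a per-scan coefficient of variation with independent errors, measurement error in an individual change is √(18² + 18²) = 25.5% with one baseline scan, against √(18² + 18²/2) = 22.0% with two.
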